The research studies in this application are expected to provide a detailed knowledge about the brain abnormalities in patients whose SD symptoms are combined with VT. Only by studying patients with different SD manifestations within the same study, we will be able to fully characterize the range of shared and distinct brain abnormalities in these patient populations and further correlate our findings with the results of their treatment effects. The knowledge gained from these studies is important because we will be able to identify neuroimaging biomarkers differentiating SD and SD/VT, which will be critical for improvement of accuracy of diagnosis of these related and often misdiagnosed disorders. Collectively, the expected results of the proposed studies will be critical for elucidation of pathophysiological mechanisms underlying SD and VT, which will serve as basis for the development of new criteria for detection, diagnosis and therapy of these patients. It is also anticipated that the potential novelty of the findings will facilitate understanding of the pathophysiological mechanisms of other forms of dystonia and tremor.

INCLUSION OF WOMEN AND MINORITIES

SD is reported to occur predominantly in women (up to 79%) and in Caucasians. Therefore, a higher percentage of Caucasian women are expected to participate in the proposed studies.

Some minority groups (Asians and American Indians) are poorly represented because limited information is available on the frequency of SD in these groups. For that reason, these minority groups may not be common in the patient populations involved in these studies. Every effort will be made to recruit minorities through the advertisements at the National Spasmodic Dysphonia Association and through the otolaryngologists serving areas of large minority populations.

INCLUSION OF CHILDREN

SD is a disorder of adult onset, usually first occurring after 40 years of age. Therefore, children will not be included in this study.

BIBLIOGRAPHY AND REFERENCES CITED

Adler CH (2000) Strategies for controlling dystonia. Overview of therapies that may alleviate symptoms. *Postgrad Med* 108:151-152, 155-156, 159-160.

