1.3.1 Study #1: Mapping disorder-specific brain activation in patients with SD vs. SD/VT using fMRI during symptomatic voice and speech production. We will use a sparse-sampling event-related BOLD fMRI design on a 3.0 Tesla Philips MRI scanner. We already successfully used this design for the investigations of voice and other laryngeal behaviors (Loucks et al., 2007; [name] et al., 2007; [name] et al., 2009; [name] and Ludlow, 2010). Brain activity will be studied during production of 10 symptomatic speech sentences (e.g., "We eat eels every day", "Sam has a rabbit in his hand") and syllables (repetitive vowel /i/ and continuous vowel /i/). In the scanner, subjects will listen to an auditory example of the task presented in a pseudorandomized order and reproduce it within the 5-s interval of the 'silent' period of scanning, only after which a 2-s image acquisition will follow, while the subjects remain silent and motionless. A resting condition without auditory presentation will serve as a baseline. Four scanning sessions will be acquired with a total of 36 experimental trials and 24 baseline conditions. Structural MRI will be acquired for an anatomical reference.

Data analysis will follow the similar processing pipeline as previously employed by us using AFNI software ([name] et al., 2007; [name] et al., 2009; [name] and Ludlow, 2010). Following initial data processing, the task-related responses will be analyzed using multiple linear regression with a single regressor for each task convolved with a canonical hemodynamic response function. Baseline drifts will be modeled using quadratic polynomials in time for each separate imaging run, and motion parameter estimates will be used as additional regressors of no interest in the multiple regression analysis. To account for disorder-specific vocal motor differences between SD and SD/VT groups, such as adductor and abductor voice breaks and shakiness, respectively, we will include the number of voice breaks and severity of voice tremor as variables in a within-group statistical analysis. Quantitative measures of SD and VT symptoms will be derived from the *Study 1.3.3* within this Aim. The correction of individual statistical parametric maps for multiple comparisons will be performed using Monte-Carlo simulations (Forman et al., 1995), which will identify a minimum cluster size at a voxelwise threshold of 0.005 at overall significance level of a corrected $p \leq 0.025$.

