Recent tolerability and efficacy trials of sodium oxybate in patients with ET, myoclonus-dystonia and post-hypoxic myoclonus have established satisfactory tolerability and improvement of disorder symptoms over 50% as measured by blinded videotape review ([name] et al., 2005a; [name] et al., 2005b; Arpesella et al., 2009). Our preliminary data further demonstrate that sodium oxybate significantly improves symptoms of SD and VT, with SD/VT patients receiving greater benefits compared to SD patients. Patients with movement disorders usually take 1-2 gm of the drug given three times daily compared to patients with narcolepsy, who take between 4.5 and 9 gm of the drug at night ([name] et al., 2005a; [name] et al., 2005b; Arpesella et al., 2009). Sodium oxybate works quickly, within 45 minutes of oral administration and its effects are visible in the office. Each dose typically lasts 3½-4 hours. Possible side effects include dose-dependent sedation and dizziness, which, however, have marked individual variability. In summary, sodium oxybate may hold promise of a potentially new treatment option for SD and SD/VT, especially for those who have limited symptom improvement following botulinum toxin injections.

2.2.2 Preliminary Data.

I. Sodium oxybate is effective and well tolerated in SD and SD/VT patients. In a pilot study, we evaluated 2 patients with SD and 4 patients with SD/VT. All patients were symptomatic at the time of examination. Three patients were treated with botulinum toxin injections with the last injection received at least 3 months prior to the study participation; botulinum toxin treatment in the other 3 patients was not successful. All patients reported significant relief of their symptoms with ingestion of alcohol.

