2.3 Research Design

The following 2 groups of patients will participate in the proposed studies of Specific Aim #2: (1) SD patients, and (2) SD/VT patients. Because sodium oxybate has been shown to be effective in patients with movement disorders who self-report symptom improvement after alcohol intake, only ethanol-responsive patients will be recruited for the purposes of these studies. We estimate that 60% of ethanol-responsive patients per group, who participated in the studies in Specific Aim #1, will also participate in the studies in Specific Aim #2. Both ADSD and ABSD patients will be included and closely matched with ADSD/VT and ABSD/VT patients. Patients will be identified according to the screening and detailed examinations as described in Specific Aim #1. In this Specific Aim, we will (1) evaluate the central effects of sodium oxybate in SD and SD/VT patients to determine the relationship between improved clinical symptoms and modulated brain function, and (2) examine the extent of central effects from the combined use of sodium oxybate and botulinum toxin treatments as an alternative treatment schedule for patients with limited benefits.

2.3.1 Study #1: Mapping central effects of sodium oxybate treatment in patients with SD and SD/VT using fMRI during symptomatic speech production. Similar to the fMRI study under Specific Aim #1, we will use a sparse-

sampling event-related BOLD fMRI design during symptomatic voice and speech production on a 3.0 Tesla Philips MRI scanner. Each patient will participate in 2 fMRI sessions, before and after treatment with sodium oxybate. All recruited patients will have to be symptomatic; if they are treated with botulinum toxin injections, they may be included only if they are symptomatic at the end of their botulinum toxin treatment cycle. During each scanning session, the patient will be asked to perform short English sentences as well as repetitive and continuous vowel /i/, designed to elicit SD and VT symptoms. Four scanning sessions will be acquired with a total of 36 experimental trials and 24 baseline resting conditions. Structural MRI will be acquired for an anatomical reference.

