Following the initial (baseline) fMRI session, patients will receive an individualized tolerable and efficacious single dose of sodium oxybate, given orally in the office. Patients' symptoms will be evaluated and videotaped one hour after receiving this dose with the immediately followed-up second fMRI session, during which the patients will be asked to produce the same tasks performed during the pre-treatment fMRI study. Patients' post-treatment scans will be compared to their pre-treatment scans to identify differences in brain activation abnormalities due to the effects of sodium oxybate treatment. Voice and speech production during both scanning sessions will be digitally recorded for acoustical analysis and correlations with the central effects of the treatment.

Data analysis. Using AFNI software, fMRI data analysis will include initial pre-processing followed by analysis of the task-related responses using multiple linear regression with a single regressor for each task convolved with a canonical hemodynamic response function, as described above in *1.3.1 Study of Specific Aim #1*. For group analysis, a two-way ANOVA will be conducted with subject as a random factor and task as fixed factor (corrected $p \leq 0.025$). Conjunction analysis at a cluster significance threshold of $p < 0.005$ will determine common and distinct regions of activation within the patient group during task production in the pre- and post-treatment fMRI sessions. Finally, pre- and post-treatment neuroimaging findings will be correlated with the behavioral data derived from acoustical analysis of voice and speech recordings.

Additionally, to determine the extent of sodium oxybate effects on speech network dynamics, we will re-examine functional and effective network connectivity using the same PPI and DCM procedures as described in the *Study 1.3.1*.

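### The post-dose scans have no sedation measure and no stated rule for unspoken trials, so drowsiness or silence could be read as normalized brain activation

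*Combined protocol and SAP*

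**What the plan says.** Section 2.2.1 (Review of Relevant Literature) says of the drug: "Possible side effects include dose-dependent sedation and dizziness, which, however, have marked individual variability". It puts onset within 45 minutes and duration of a dose at 3½ to 4 hours.

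In Section 2.3.1 (Study #1 of Specific Aim #2), after the baseline scan, "patients will receive an individualized tolerable and efficacious single dose of sodium oxybate, given orally in the office". Then: "Patients' symptoms will be evaluated and videotaped one hour after receiving this dose". The second fMRI session follows at once. The stated purpose of the comparison is: "Patients' post-treatment scans will be compared to their pre-treatment scans to identify differences in brain activation abnormalities due to the effects of sodium oxybate treatment".

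On trial numbers: "Four scanning sessions will be acquired with a total of 36 experimental trials and 24 baseline resting conditions". I read the four sessions as runs within one visit, so each scan has 36 task and 24 rest trials. Under Section 1.3.1, whose design 2.3.1 follows, the patient hears an example and reproduces it within a 5-second silent window, and one 2-second acquisition follows.

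The first-level analysis is "multiple linear regression with a single regressor for each task convolved with a canonical hemodynamic response function", done as in Section 1.3.1. That section adds quadratic drift and says "motion parameter estimates will be used as additional regressors of no interest". The group model in 2.3.1 is a two-way ANOVA with subject random and task fixed.

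Speech is recorded in the scanner at both sessions. The stated uses are acoustic analysis and correlation with the central effects. Study 2.3.2 reuses the design and the pipeline.

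**The concern.** The expected result of Aim 2 is that abnormally high activation falls after the drug. A patient who is drowsy, or who misses the speaking window, would also show less task activation. The bias therefore runs in the direction of the hypothesis.

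Three features of the plan leave it open. The one-hour evaluation covers symptoms and names no rating of sedation or alertness. The Potential Risks section covers nasolaryngoscopy, MRI and loss of data, so sedation is not captured as safety data there either. No rule says what happens to a trial without speech. And there is no placebo or untreated repeat scan against which a non-specific fall could be recognized.

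At stake is the mechanistic conclusion. Sedation is itself an effect of the drug, so a pre/post difference would still be drug-related. The error would be to read general sedation, or simple non-performance, as correction of the disorder's abnormal activation.

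**Working it through.** **Timing.** The drug acts from within 45 minutes to 3½–4 hours after a dose (2.2.1). Scan 2 starts about 1 hour after the dose (2.3.1), and a scanning session lasts up to 2 hours (Protection of Human Subjects). So scan 2 runs from about 1 hour to at most about 1 + 2 = 3 hours, inside the stated period of action. For scan 3 (2.3.2) the patient takes the drug three times daily, but no dose-to-scan interval is given.

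**Effect on the task estimate.** With one acquisition per trial and a single regressor, and assuming that a missed trial gives no task response:

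expected estimate = true estimate × (1 − m/36), where m is the number of missed trials.

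A least-squares check on 60 volumes (36 task, 24 rest) with quadratic drift gives the same fractions to rounding.

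| Missed trials m | m/36 | Single regressor, fraction of true value | Separate regressor for unspoken trials |
|---|---|---|---|
| 2 | 5.6% | 0.94 | 1.00 |
| 4 | 11.1% | 0.89 | 1.00 |
| 6 | 16.7% | 0.83 | 1.00 |
| 9 | 25.0% | 0.75 | 1.00 |

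This pools all 36 trials. Each task has its own regressor and the split of trials by task is not stated, so misses concentrated in one task would weigh more on that task.

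**What that could do to a test.** The plan's 22 per group cannot be rebuilt, because the standard deviation of the 49% change is not given. A paired t-test with n = 22, 80% power and two-sided 0.025 corresponds to a standardized change of 0.70. For scale only, I take the patient value 0.63 ± 0.16 (% signal change) from the sample-size paragraph of 1.3.1. I assume that true activation is unchanged, that misses occur only after the dose, that every patient misses the same number, and that the pre/post correlation is r.

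- SD of change = 0.16 × √(2(1 − r)). At r = 0.5 this is 0.16.
- Spurious standardized change = 0.63 × (m/36) / SD of change. At m = 4 and r = 0.5: 0.07 / 0.16 = 0.44.
- Misses that equal the detectable effect = 36 × 0.70 × SD of change / 0.63. This gives 7.6, 6.4 and 4.0 trials at r = 0.3, 0.5 and 0.8.

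Chance of a significant difference with n = 22, against a nominal 0.025:

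| r | Response on missed trial | m = 2 | m = 4 | m = 6 |
|---|---|---|---|---|
| 0.3 | none | 0.08 | 0.27 | 0.58 |
| 0.5 | none | 0.10 | 0.38 | 0.74 |
| 0.8 | none | 0.24 | 0.79 | 0.99 |
| 0.3 | half | 0.04 | 0.08 | 0.16 |
| 0.5 | half | 0.04 | 0.10 | 0.21 |
| 0.8 | half | 0.07 | 0.24 | 0.52 |

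The rows with half the response allow for listening to the auditory example, which can evoke activity even when no speech follows. The test here is for one region, not the planned corrected voxelwise analysis. The documents give no miss rate, so these figures show sensitivity, not expected bias.

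**Pilot measure.** The pilot's 49% in 2.2.2 is a fall in the number of significantly active voxels. Such a count also falls when the task estimate falls.

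**The case against.** The plan is not without protection. The dose is chosen to be tolerable, and Section 2.2.2 reports that all six pilot patients tolerated the drug well. Each scan has its own rest baseline, so a change that affects task and rest alike partly cancels. Patients are seen and videotaped just before scan 2, so marked drowsiness might be noticed. Brain change is to be correlated with acoustic change, which is some check on a purely non-specific fall. And the speech recordings would show silent trials if anyone looked.

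All of this stands as mitigation, and none of it closes the gap. Tolerable does not mean unsedated when the effect is dose-dependent and varies between patients. The rest baseline does not correct for speech that did not happen. If voice breaks are counted per session, silent trials lower both the breaks and the activation, and so could produce the expected correlation. The reassurance on task performance under Protection Against Risk rests on earlier imaging experience and does not mention sodium oxybate.

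A reader might go further and infer that SD/VT patients need higher doses, are therefore more sedated, and so imitate the hypothesis of greater modulation in that group. The documents do not support this. Section 2.2.2 says that dose varied between patients and tracked the alcohol dose needed for a similar result. It reports no difference by group, and with individually variable sensitivity a higher dose need not mean more sedation.

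A reader might also take it that the plan states that silent trials are kept as performed. It does not. That is the plain consequence of the model as written, and an unstated processing step could avoid it.

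**Conclusion.** The concern holds as a gap in measurement and modelling, worth closing before the first post-dose scan. Named sedation, a scan inside the period of drug action, no sedation measure and a single regressor per task together leave a route by which non-performance or non-specific sedation could be reported as normalization.

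The size is conditional. With no response on missed trials, the task estimate falls by about 6% to 25% for 2 to 9 misses of 36, and by less where listening still evokes a response. All Aim 2 patients (25 per group, 50 in total) are potentially exposed at scan 2. That is not a claim that all are affected, and the documents do not show that any bias will occur. Exposure at scan 3 cannot be judged, because the interval from dose to scan is not stated. The point does not depend on the sample-size figure.

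**What to change.** In Section 2.3.1, carried to 2.3.2:

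1. Use the in-scanner recordings to code each trial in each session as spoken or not. Model unspoken trials with a separate regressor of no interest, and report their number per session and group. In the illustration this restores the task estimate, but it does not deal with sedation on trials that are spoken.
2. Record a brief sedation and dizziness rating at every scan, including baseline, and the time since dose at each post-dose scan. Report both beside the pre/post and the SD versus SD/VT results. The 12 patients per group carried over from Aim 1 use their Aim 1 scan as baseline, so the rating and the trial coding must apply to that scan too.
3. Label any analysis adjusted for change in sedation as exploratory. Sedation is a drug effect and may lie on the treatment pathway, so adjustment can remove real effect.

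The cost is a one-line form per scan, time to code recordings that are already planned, and slightly fewer usable trials in drowsy patients. The trial coding could be done later from the recordings. The ratings cannot be recovered once the scans are done.

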To date, oral medications are known to provide little relief from SD and VT symptoms, and, thus, these patients are not systematically prescribed any medications (Adler, 2000). However, some patients report anecdotal benefits from taking lorazepam, clonazepam, diazepam, gabapentin, as well as some receive anti-depressants and anti-anxiety drugs to cope with their disorder-associated depression and anxiety. Recently, a series of clinical trials have reported significant beneficial effects of sodium oxybate on symptom improvement in treatment-refractory hyperkinetic movement disorders, including dystonia and ET ([name] et al., 2005a; [name] et al., 2005b; Arpesella et al., 2009). This medication seems to target more efficiently the tremor symptoms. Hence, it is possible that it may represent an alternative treatment option for SD/VT patients, whose symptoms are not fully responsive to botulinum toxin treatment.

However, despite remarkable improvement of symptoms in patients with movement disorders, the central effects of sodium oxybate also remain unknown. The absence of such information is a significant problem because it prevents the development of a scientific rationale for the use of a potentially beneficial novel pharmaceutical agent for the treatment of SD and VT. The objective of this aim is, therefore, to identify the mechanisms of central action of a promising novel medication, sodium oxybate, in SD and SD/VT patients as well as to determine the extent of central effects of a combined use of sodium oxybate and botulinum toxin treatments. Our working hypothesis is that the greater beneficial effects of sodium oxybate treatment in SD/VT patients compared to SD patients are due to a greater extent of modulation of their abnormal brain activation. This hypothesis has been formulated based on our preliminary data and will be tested using the experimental approach of fMRI during symptomatic speech production before and after treatment in SD and SD/VT patients, who report improvement of their symptoms after alcohol intake. The rationale for these studies is that the explanation of central mechanisms of action of sodium oxybate in SD and VT patients would help establish a scientific rationale for this drug as a new treatment option for patients who have failed other therapies.

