II. Sodium oxybate modulates abnormally increased activation in SD and SD/VT patients. Using a sparse-sampling BOLD fMRI design and symptomatic speech production, we examine the effects of sodium oxybate on brain activation abnormalities in 3 SD and SD/VT patients to evaluate the mechanisms of central action of this novel pharmacological agent. Compared to healthy controls, before treatment, all patients exhibited typically increased brain activation during symptomatic speech production ($p \leq 0.05$, corrected) (Fig. 3-I) similar to abnormalities described before (Haslinger et al., 2005; Ali et al., 2006; [name] and Ludlow, 2010) and in our 1.2.2 *Preliminary Studies* above. After treatment, patients' brain activation was significantly attenuated and followed a nearly normal pattern present during normal speech production, with only few regions remaining hyperactive ($p \leq 0.05$, corrected) (Fig. 3-II). A two-tailed paired *t*-test calculation using the measure of the total number of significantly active brain voxels before and after treatment in patients showed that the drug-induced attenuation of abnormal functional activation was in average 49% ($p = 0.017$) (Fig. 3-III). Specifically, sodium oxybate treatment significantly decreased and normalized abnormally elevated brain activity in the prefrontal, premotor and auditory cortices as well as in the basal ganglia, thalamus, and cerebellum. In 1.2.2 *Preliminary Studies* presented above, we found these regions to have a greater extent of abnormal activation in SD/VT patients compared to SD patients.

[figure not shown]

Figure 3 depicts differences in brain activation in SD and SD/VT compared to healthy controls before (I) and after (II) treatment with sodium oxybate (voxelwise $p \leq 0.05$, corrected). Panel (III) shows significantly decreased number of hyperactive brain voxels after the treatment compared to the before treatment baseline in patients ($p = 0.017$).

Collectively, our preliminary data indicate that sodium oxybate is effective in SD patients and especially in those who present with a VT component. Furthermore, our data suggest that the effects of sodium oxybate treatment are exerted through the modulation of overly increased brain activation.

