Study population and Sample size. To our knowledge the central effects of sodium oxybate has not been reported. Therefore, to estimate the number of patients to be included in this study, we reviewed our pilot fMRI study in SD and SD/VT patients. Compared to baseline, we found an average of 49% reduction of overly increased brain activation after treatment with sodium oxybate. Power analysis determined a sample size of 22 patients in each group to have 80% power at 0.025 to detect changes in brain activation when comparing before and after treatment conditions. We propose to recruit 25 ethanol-responsive SD and SD/VT subjects per group to account for the subjects' dropout possibilities and to increase statistical power.

2.3.2 Study #2: Evaluation of combined central effects of sodium oxybate and botulinum toxin treatments in patients with SD and SD/VT using fMRI during symptomatic speech production. In this study, we will use the same fMRI design as used in the Similar to *Studies 1.3.1* and *2.3.1* to examine the combined effects of sodium oxybate and botulinum toxin on brain activation changes due to the treatment.

We estimate that about 40% of all recruited patients (mostly with ADSD) will report some benefits from botulinum toxin injections. These patients will be enrolled in this study and will undergo the third scanning session after receiving their botulinum toxin treatment. They will be asked to take their individualized dose of sodium oxybate T.I.D. after the completion of the *Study 2.3.1* and until the end of this study. We predict that about 60% of SD (typically ABSD) and SD/VT patients recruited to the *Study 2.3.1* will report limited, if any, benefits from botulinum toxin treatment. These patients will, therefore, be replaced with newly recruited patients, whose symptoms do response to both alcohol intake and botulinum toxin treatment. Thus, at the time of this study, all patients will be treated with both sodium oxybate and botulinum toxin injections. The decision of whether sodium oxybate should be continued after the completion of all studies in this proposal will be made by the patient and his/her referring physician.

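### The Aim 2 activation analysis compares patients only with their own pre-drug scans, so it cannot show that the change is in abnormal activation

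*Combined protocol and SAP*

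**What the plan says.** The Aim 2 hypothesis, in Specific Aims and again in section 2.1, is that the larger benefits in SD/VT than in SD "are due to a greater extent of modulation of their abnormal brain activation". The sample-size paragraph of section 2.3.1 rests on an average 49% "reduction of overly increased brain activation after treatment with sodium oxybate".

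The design in section 2.3 has no controls: "The following 2 groups of patients will participate in the proposed studies of Specific Aim #2: (1) SD patients, and (2) SD/VT patients". The comparison in section 2.3.1 is within patient: "post-treatment scans will be compared to their pre-treatment scans to identify differences in brain activation abnormalities due to the effects of sodium oxybate treatment". For the group model, "a two-way ANOVA will be conducted with subject as a random factor and task as fixed factor"; a conjunction analysis then looks for common and distinct regions within the patient group across the two sessions. Imaging findings are to be correlated with acoustic voice measures, and connectivity is to be re-examined with the PPI and DCM procedures of section 1.3.1.

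The pilot in section 2.2.2 did use an outside reference. Figure 3 shows patients "compared to healthy controls before (I) and after (II) treatment with sodium oxybate". Section 2.2.1 says of the drug: "Possible side effects include dose-dependent sedation and dizziness". Section 2.5, on potential problems, discusses neither sedation nor repeat scanning.

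**The concern.** Activation is abnormal, or overly increased, only relative to healthy speakers. An analysis that contains only patients can show that activation changed after the drug. It cannot show that the change was in the activation that set these patients apart. The on-drug scan always follows the off-drug scan, with the same tasks repeated, and the drug can sedate. A general fall in task response would therefore give the same significant pre-to-post result as a correction of the disorder.

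At stake is the mechanistic conclusion. The scans would remain usable, but a positive result from the planned activation analysis would not support the statement that the drug modulates abnormal activation.

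**Working it through.** **1. Claim and analysis side by side.**

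| Element | Reference used |
|---|---|
| Hypothesis (Specific Aims, 2.1) | abnormal activation, so healthy controls |
| Sizing (2.3.1) | overly increased activation, so healthy controls |
| Pilot (2.2.2, Figure 3) | healthy controls, before and after drug |
| Aim 2 ANOVA (2.3.1) | none; subject and task only |
| Aim 2 conjunction (2.3.1) | the same patients' other session |

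The missing reference is available. Aim 1 scans 20 controls on the same scanner with the same type of task (sections 1.3.1 and 2.3.1).

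**2. The plan's own figure.** Section 2.3.1 states 22 patients per group for 80% power at 0.025. The SD of the change is not given, so I back-calculated the standardised change dz = t/√n from the pilot's two-tailed paired p = 0.017.
- Pilot n = 3: t = 7.57, dz = 7.57/√3 = 4.37, which needs 4 patients.
- Pilot n = 6 (if the pilot wording means 3 per group): t = 3.52, dz = 3.52/√6 = 1.44, which needs 8.

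Neither gives 22. That is a separate matter: without the SD, 22 is unsupported rather than shown to be wrong. Solving in reverse, a paired t-test with n = 22, two-sided 0.025 and 80% power implies dz = 0.70. I use that only as a scale.

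**3. How often a purely non-specific fall would be significant.** The formula is P(|T| > t crit), with T noncentral t on n − 1 degrees of freedom and noncentrality dz·√n. For n = 25, t crit = 2.39; at half the design effect, dz = 0.35 and noncentrality = 0.35 × 5 = 1.75.

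| Non-specific fall as share of 0.70 | dz | n = 22 | n = 25 |
|---|---|---|---|
| 0 | 0 | 2.5% | 2.5% |
| 25% | 0.175 | 7% | 8% |
| 50% | 0.35 | 24% | 28% |
| 75% | 0.525 | 53% | 60% |
| 100% | 0.70 | 80% | 86% |

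Likewise, if repeat scanning alone shifted activation by an assumed dz of 0.2 to 0.5, the test with n = 25 would be positive 10% to 55% of the time.

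**4. The pilot measure.** The pilot counted significantly active voxels. Assume voxel z-values centred on zero with spread s, threshold c, and a uniform amplitude drop d. The reduction in the count is 1 − P(Z > c/[s(1 − d)]) / P(Z > c/s). With s = 1.5 and c = 2.58, drops of 5%, 10% and 15% give 18%, 34% and 50% fewer active voxels. For a 15% drop, over s = 1.2 to 2.0 and c = 1.96 to 2.81, the range is 24% to 69%. None of these inputs is in the documents. The exercise shows only that a voxel count can fall steeply without regional specificity.

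**5. Which added test can discriminate.** Take the means in section 1.3.1 as illustrative levels: 0.63 inside abnormal regions and 0.39 outside.
- Absolute contrast under a uniform 15% fall: 0.63 × 0.15 − 0.39 × 0.15 = 0.0945 − 0.0585 = +0.036. At 38%: 0.2394 − 0.1482 = +0.091. A uniform fall passes.
- Comparison with controls: (0.63 − 0.39)/0.63 = 38%, so a uniform 38% fall takes the SD mean to the control mean. A uniform fall can pass this too.
- Proportional contrast: 15% inside minus 15% outside = 0. A uniform fall does not pass.

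**The case against.** The plan contains more than the activation ANOVA. The PPI and DCM procedures borrowed from section 1.3.1 are seeded from regions of abnormal function with underlying structural change, and DCM compares patients with controls. A reader might infer that Aim 2 has no link to controls anywhere; the documents do not support that. What stands is narrower: section 2.3.1 does not say that post-drug scans will be compared with controls, and the activation analysis, on which the study is sized, names no such step.

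The hypothesis is also a contrast, with greater modulation in SD/VT than in SD. A fall common to both groups would not by itself support it. But the ANOVA as described lists neither group nor session, so that internal contrast is not written in.

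There are partial safeguards. Each session has resting baseline trials, which remove a shift common to task and rest but not a smaller task response. The acoustic correlations tie brain change to voice change, but something acting on both could produce them. The documents add that side effects vary markedly between patients and that the dose is individualised to be tolerable.

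A reader might go further and infer that sedation or practice explains the pilot's 49% reduction. Nothing in the documents shows this: no size is given for either effect.

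**Conclusion.** The point holds for the activation analysis. Followed as written, section 2.3.1 can establish a change after the drug but not that the change lies in abnormal activation. It does not hold for Aim 2 as a whole, because the connectivity procedures carry an implicit, though unstated, control reference.

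That the reference is missing rests on the text alone. The size of the resulting error cannot be derived from the documents. The 28%, the 10% to 55% and the 24% to 69% are illustrations that depend on the assumed dz of 0.70, the assumed repeat-scan shifts and the assumed voxel distribution. They show that misreading is possible, not how likely it is.

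The Aim 1 controls cannot settle everything. They have at most two visits, one of them screening, and hence one undrugged scan. They can locate abnormal regions and give a normal level, but they cannot measure sedation or repetition.

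**What to change.** Add to the data analysis of section 2.3.1:

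- **(a) Regions.** Define abnormal regions from the Aim 1 patient-versus-control maps. For the 12 patients per group who also take part in Aim 1, leave each patient out of the map applied to that patient, so that regression to the mean does not produce a fall.
- **(b) Main test.** Test whether the proportional, not absolute, pre-to-post change is greater inside than outside those regions. Take the outside regions from those that respond to the task, since a proportional change is unstable where baseline is near zero.
- **(c) Supporting comparison.** Compare pre-drug and post-drug patients with the 20 Aim 1 controls in those regions.
- **Wording.** Reserve the conclusion that abnormal activation was modulated for a positive result on (b). Report (c) as support for normalisation only.
- **Limitation.** State that the fixed off-drug then on-drug order and once-scanned controls cannot separate a disorder-specific drug effect from repeat-scan effects or sedation. A positive (b) argues against a uniform fall, not against sedation that acts unevenly across regions.

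The text on baseline timing must also be reconciled. Section 2.3.1 describes dosing after the baseline session, whereas Protection of Human Subjects, section 1a, lets 12 patients per group reuse their Aim 1 scan as baseline, with no stated interval to the post-drug scan.

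The cost is a little more analysis, with no new scans, and a narrower conclusion. The power of (b) cannot be given, because the documents state no variance for the change. I do not propose changing the scan order: that would alter when the drug is given relative to section 2.3.1, and could reach only the 13 newly recruited of 25 patients per group.
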